### **8.7.3 Interim Analysis**

No interim analysis is planned for this study.

The safety monitoring will be conducted by the independent data monitoring committee (IDMC). The frequency of the safety reviews will be defined in the IDMC charter. Minutes from the open meetings of the IDMC will be provided if requested by regulatory agencies. The recommendation of whether to stop the study for safety will be reached by the IDMC based on their review of safety data with treatment information. The function and membership of the IDMC will be described in the IDMC charter.

### **8.7.4 Other Statistical/Analytical Issues**

Not applicable.

### **8.7.5 Procedure for Revising the Statistical Analysis Plan**

If the SAP needs to be revised after the study starts, the sponsor will determine how the revision impacts the study and how the revision should be implemented. The details of the revision will be documented and described in the clinical study report.

## **10 PROCEDURES AND INSTRUCTIONS (ADMINISTRATIVE PROCEDURES)**

### **10.1 Changes to the Protocol**

Any change to the protocol requires a written protocol amendment or administrative change that must be approved by the sponsor before implementation. Amendments specifically affecting the safety of subjects, the scope of the investigation, or the scientific quality of the study require submission to health or regulatory authorities as well as additional approval by the applicable IRBs/IECs. These requirements should in no way prevent any immediate action from being taken by the investigator, or by the sponsor, in the interest of preserving the safety of all subjects included in the study. If the investigator determines that an immediate change to or deviation from the protocol is necessary for safety reasons to eliminate an immediate hazard to the subjects, the sponsor's medical monitor and the IRB/IEC for the site must be notified immediately. The sponsor must notify the health or regulatory authority as required per local regulations.

Protocol amendments that affect only administrative aspects of the study may not require submission to health or regulatory authority or the IRB/IEC, but the health or regulatory authority and IRB/IEC (or if regionally required, the head of the medical institution) should be kept informed of such changes as required by local regulations. In these cases, the sponsor may be required to send a letter to the IRB/IEC and the Competent Authorities (or, if regionally required, the head of the medical institution) detailing such changes.

### **10.2 Adherence to the Protocol**

The investigator will conduct the study in strict accordance with the protocol (refer to ICH E6, Section 4.5).

### **10.3 Monitoring Procedures**

The sponsor's/CRO's CRA will maintain contact with the investigator and designated staff by telephone, letter, or email between study visits. Monitoring visits to each site will be conducted by the assigned CRA as described in the monitoring plan. The investigator (or if regionally required, the head of the medical institution) will allow the CRA to inspect the clinical, laboratory, and pharmacy facilities to assure compliance with GCP and local regulatory requirements. The CRFs and subject's corresponding original medical records (source documents) are to be fully available for review by the sponsor's representatives at regular intervals. These reviews verify adherence to study protocol and data accuracy in accordance with local regulations. All records at the site are subject to inspection by the local auditing agency and to IRB/IEC review.

In accordance with ICH E6, Section 1.52, source documents include, but are not limited to, the following:

- Clinic, office, or hospital charts

- Copies or transcribed health care provider notes that have been certified for accuracy after production
- Recorded data from automated instruments such as IVRS, x-rays, and other imaging reports (eg, sonograms, CT scans, magnetic resonance images, radioactive images, ECGs, rhythm strips, EEGs, polysomnographs, pulmonary function tests) regardless of how these images are stored, including microfiche and photographic negatives
- Pain, quality of life, or medical history questionnaires completed by subjects
- Records of telephone contacts
- Diaries or evaluation checklists
- Drug distribution and accountability logs maintained in pharmacies or by research personnel
- Laboratory results and other laboratory test outputs (eg, urine pregnancy test result documentation and urine dip-sticks)
- Correspondence regarding a study subject's treatment between physicians or memoranda sent to the IRBs/IECs
- CRF components (eg, questionnaires) that are completed directly by subjects and serve as their own source
- Electronic Patient-Reported Outcome by self-reported measures

#### **10.4 Recording of Data**

A CRF is required and must be completed for each subject by qualified and authorized personnel. All data on the CRF must reflect the corresponding source document, except when a section of the CRF itself is used as the source document. Any correction to entries made on the CRF must be documented in a valid audit trail where the correction is dated, the individual making the correct is identified, the reason for the change is stated, and the original data are not obscured. Only data required by the protocol for the purposes of the study should be collected.

The investigator must sign each CRF. The investigator will report the CRFs to the sponsor and retain a copy of the CRFs.

#### **10.5 Identification of Source Data**

All data to be recorded on the CRF must reflect the corresponding source documents.

#### **10.6 Retention of Records**

The circumstances of completion or termination of the study notwithstanding, the investigator (or if regionally required, the head of the medical institution or the designated representative) is responsible for retaining all study documents, including but not limited to the protocol, copies of CRFs, the Investigator's Brochure, and regulatory agency registration documents (eg, Form FDA 1572 for US sites), Investigator and Site Information Form (for non-US sites), ICFs, and IRB/IEC correspondence). The site should plan to retain study

documents, as directed by the sponsor, for at least 15 years following the completion of the study.

It is requested that at the completion of the required retention period, or should the investigator retire or relocate, the investigator contact the sponsor, allowing the sponsor the option of permanently retaining the study records.

## **10.7 Auditing Procedures and Inspection**

In addition to routine monitoring procedures, the sponsor's Clinical Quality Assurance department conducts audits of clinical research activities in accordance with the sponsor's SOPs to evaluate compliance with the principles of ICH GCP and all applicable local regulations. If a government regulatory authority requests an inspection during the study or after its completion, the investigator must inform the sponsor immediately.

## **10.8 Handling of Study Drug**

All study drug will be supplied to the principal investigator (or a designated pharmacist) by the sponsor. Drug supplies must be kept in an appropriate secure area (eg, locked cabinet) and stored according to the conditions specified on the drug labels. The investigator (or a designated pharmacist) must maintain an accurate record of the shipment and dispensing of the study drug in a drug accountability ledger, a copy of which must be given to the sponsor at the end of the study. An accurate record of the date and amount of study drug dispensed to each subject must be available for inspection at any time. The CRA will visit the site and review these documents along with all other study conduct documents at appropriate intervals once study drug has been received by the site.

All drug supplies are to be used only for this study and not for any other purpose. The investigator (or site personnel) must not destroy any drug labels or any partly used or unused drug supply before approval to do so by the sponsor. At the conclusion of the study and as appropriate during the study, the investigator (or a designated pharmacist) will return all used and unused drug containers, drug labels, and a copy of the completed drug disposition form to the sponsor's CRA (or designated contractor) or, when approval is given by the sponsor, will destroy supplies and containers at the site.

## **10.9 Publication of Results**

All manuscripts, abstracts, or other modes of presentation arising from the results of the study must be reviewed and approved in writing by the sponsor in advance of submission pursuant to the terms and conditions set forth in the executed Clinical Trial Agreement between the sponsor/CRO and the institution/investigator. The review is aimed at protecting the sponsor's proprietary information existing either at the date of the commencement of the study or generated during the study.

The detailed obligations regarding the publication of any data, material results, or other information generated or created in relation to the study shall be set out in the agreement between each investigator and the sponsor or CRO, as appropriate.

## **10.10 Disclosure and Confidentiality**

The contents of this protocol and any amendments and results obtained during the study should be kept confidential by the investigator, the investigator's staff, and the IRB/IEC and will not be disclosed in whole or in part to others, or used for any purpose other than reviewing or performing the study, without the written consent of the sponsor. No data collected as part of this study will be used in any written work, including publications, without the written consent of the sponsor. These obligations of confidentiality and non-use shall in no way diminish such obligations as set forth in either the Confidentiality Agreement or Clinical Trial Agreement executed between the sponsor/CRO and the institution/investigator.

All persons assisting in the performance of this study must be bound by the obligations of confidentiality and non-use set forth in either the Confidentiality Agreement or Clinical Trial Agreement executed between the institution/investigator and the sponsor/CRO.

## **10.11 Discontinuation of Study**

The sponsor reserves the right to discontinue the study for medical reasons or any other reason at any time. If a study is prematurely terminated or suspended, the sponsor will promptly inform the investigators/institutions and regulatory authorities of the termination or suspension and the reason(s) for the termination or suspension. The IRB/IEC will also be informed promptly and provided the reason(s) for the termination or suspension by the sponsor or by the investigator/institution, as specified by the applicable regulatory requirement(s).

The investigator reserves the right to discontinue the study should his/her judgment so dictate. If the investigator terminates or suspends a study without prior agreement of the sponsor, the investigator should inform the institution where applicable, and the investigator/institution should promptly inform the sponsor and the IRB/IEC and provide the sponsor and the IRB/IEC with a detailed written explanation of the termination or suspension. Study records must be retained as noted above.

## **10.12 Subject Insurance and Indemnity**

The sponsor will provide insurance for any subjects participating in the study in accordance with all applicable laws and regulations.

## 11 APPENDICES

### Appendix 1      **Response Evaluation Criteria in Solid Tumors (RECIST) 1.1**

Tumor response assessments in this clinical study will use Response Evaluation Criteria in Solid Tumors (RECIST 1.1) based on the 2009 article by Eisenhauer et al entitled *New Response Evaluation Criteria in Solid Tumors: revised RECIST guideline (version 1.1)* ([Eisenhauer, et al., 2009](#)).

The sole modification to RECIST 1.1 to be implemented in this study is that chest x-rays may not be used to follow disease; only CT scans may be used to follow chest disease. As required by RECIST 1.1, the protocol states that the minimum duration of stable disease is 7 weeks following the date of first dose of study drug.

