### *During Treatment Phase*

CT/MRI scans of, chest, abdomen, pelvis, and other known sites of disease plus any areas of newly suspected disease will be performed using the same methodology as at screening every 6 weeks  $\pm$ 1 week, following the start of treatment on Cycle 1 Day 1 during the chemotherapy treatment period until Week 18. Following completion of the chemotherapy treatment period (ie, after Week 18), the frequency of tumor assessments will be every 9 weeks  $\pm$ 1 week until Week 54  $\pm$ 1 week. Thereafter, they will be performed every 12 weeks  $\pm$ 2 weeks until documentation of PD. At any point, scans should be performed earlier than the scheduled time point, if clinically indicated.

An initial assessment of CR or PR according to RECIST 1.1 must be confirmed by IIR not less than 4 weeks after the initial response. The same methodology (CT or MRI) and scan acquisition techniques (including use or nonuse of IV contrast) as was used for the screening assessments should be utilized across all time points to allow consistent comparison of lesions. After treatment discontinuation for a reason other than PD, tumor assessments should continue to be performed as per the tumor assessment schedule until documentation of progression or start of a new anticancer agent. Screening CT scans should be performed with oral and iodinated intravenous contrast and MRI scans should be performed with intravenous gadolinium chelate. Post-screening scans may be performed without contrast if a medical contraindication develops while on study treatment. If iodinated intravenous contrast is contraindicated, chest CT should be done without intravenous contrast. MRI should be performed for all other body regions (with gadolinium unless contraindicated (eg, severe renal dysfunction).

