**Table 5 Schedule of Assessments in Study E7080-G000-230 – Randomization Phase**

Phase	Prerandomization		Randomization a (All cycles are 21 days in duration)																		
	Screening b	Baseline c	Treatment d															Off-Tx	Follow-up e		
Period	1	2	3	4	5	6	7	8	9	10	11	12	13	14	15	16	17	18+			
Visit	1	2	3	4	5	6	7	8	9	10	11	12	13	14	15	16	17	18+			
Cycle			Cycle 1			Cycle 2			Cycle 3			Cycle 4			Cycle 5			Cycle 6-X			
Day	-28 to -2	-1	1	8	15	1	8	15	1	8	15	1	8	15	1	8	15	1			
Procedures/Assessments																					
Palatability Questionnaire g			X																		
Tumor assessments: CT/MRI f	X		CT chest and CT/MRI of other areas of known disease at Screening plus any areas of newly suspected disease should be performed every 6±1 week or sooner if clinically indicated until Week 18±1 week, then every 9±1 weeks until Week 54±1 week. Thereafter, to be performed every 12±2 weeks until documentation of PD.															X			
Brain CT/MRI f	X		Brain scans will be performed at screening as clinically indicated, and thereafter during treatment if clinically indicated. For subjects with protocol-eligible, treated brain metastases at Screening, brain scans should be performed at all tumor assessment time points.																		
Height t		X	X												X				X	X	X
Tanner Stage u		X																	X	X	X
Proximal Tibial growth plates x-ray t		X																X			
HRQoL		X	HRQoL will be collected on C2D1, C3D1, Week 18, C8D1, and C18D1															X			
Pharmacodynamic biomarkers v		X		X	X										X				X		
Archival tumor block or slides w			X																		
Survival x						X															X
Concomitant medications y			Throughout															X			
AEs/SAEs z			Throughout															X			

AE = adverse event, BP = blood pressure, C1D1 = Cycle 1 Day 1, C1D2 = Cycle 1 Day 2, C1D8 = Cycle 1/Day 8, C1D15 = Cycle 1 Day 15, CR = complete response, CT = computerized tomography, h = hour, HR = heart rate, HRQoL = Health-Related Quality of Life, IV = intravenous, IVRS = Interactive Voice Response System, MRI = magnetic resonance imaging, PD = progressive disease/disease progression, PK = pharmacokinetics, PR = partial response, PS =

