#### 8.7.1.1.3 EXPLORATORY ENDPOINTS

- Duration of response (DOR) by IIR is defined as the time from the date a response was first documented until the date of the first documentation of PD or date of death from any case.
- Disease control rate (DCR) by IIR is the proportion of subjects who have a best overall response of CR or PR or stable disease (SD). In this context, stable disease is defined as stable disease at  $\geq 7$  weeks after randomization to be considered best overall response.
- Clinical benefit rate (CBR) by IIR is the proportion of subjects who have best overall response of CR or PR or durable SD (duration of SD  $\geq 23$  weeks after randomization).
- Proportion of subjects who achieve complete removal of baseline lesions following completion of chemotherapy.
- Blood and tumor biomarkers will be assessed for identifying potential correlation with clinical outcomes-related endpoints.
- All efficacy endpoints above (except OS) will be evaluated by both IIR and investigator assessment using RECIST 1.1.

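### The 7-week stable-disease minimum misses an on-time Week 6 scan, the 23-week cut-off falls where no scan is scheduled, and the 7 weeks have two different starting points

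*Protocol*

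**What the plan says.** **Endpoints.** Protocol section 8.7.1.1.3, with the same rule in the synopsis, puts the SD limit for DCR at 7 or more "weeks after randomization to be considered best overall response". CBR counts a "best overall response of CR or PR or durable SD", where durable SD must last at least 23 weeks, also counted from randomization.

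**Appendix 1.** This reports, as something the protocol states, that "the minimum duration of stable disease is 7 weeks following the date of first dose of study drug".

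**Scans.** Section 8.5.1.2.1 sets a six-weekly CT/MRI interval, with a window of one week either side, and gives its starting point and span as "following the start of treatment on Cycle 1 Day 1 during the chemotherapy treatment period until Week 18". Table 5 says the scans "should be performed every 6±1 week or sooner if clinically indicated until Week 18±1 week, then every 9±1 weeks until Week 54±1 week". Table 5 also puts randomization in the Cycle 1 Day 1 column.

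**Use.** Section 7.3 lists DCR and CBR as exploratory objectives. Section 8.7.1.6.3 asks for the rate in each arm and for the between-arm difference with a two-sided 95% CI.

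**The concern.** SD can be recorded only when a scan is done. A time limit that does not match a scan window either acts as a later limit than the one written, or makes a subject's class depend on the day within the window on which the scan happened to be booked. The 7-week limit does both: for nearly every permitted first-scan day it acts as a Week 12 limit, and on the last permitted day it does not. The 23-week limit falls in a stretch with no scheduled scan. The two statements of the 7 weeks also start from different dates.

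What is at stake is whether DCR and CBR have one meaning. Two analysts following the protocol could report different rates and a different between-arm difference from the same scans.

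**Working it through.** The protocol states no DCR or CBR rate, so there is no figure to reproduce.

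**1. First scan against 7 weeks.** Nominal day 6 × 7 = 42. Window 5 × 7 = 35 to 7 × 7 = 49, which is 49 − 35 + 1 = 15 permitted days. The minimum is 7 × 7 = day 49. With randomization on Cycle 1 Day 1, 1 of the 15 days qualifies. The next window is Weeks 11 to 13.

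| Scan history | Section 8.7.1.1.3 (SD at ≥7 weeks) | Appendix 1, if duration runs to PD |
|---|---|---|
| SD on day 42, PD at Week 12 | not controlled | about 12 weeks, controlled |
| SD on day 49, PD at Week 12 | controlled | controlled |
| SD on day 42, SD at Week 12 | controlled | controlled |

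The first row differs from the second only in the scan day. It also gets opposite answers from the two parts of the protocol.

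**2. Durable SD against 23 weeks.** The Week 18 window is Weeks 17 to 19 and the Week 27 window is Weeks 26 to 28, so no scheduled scan can fall at 23 weeks. SD at Week 18 with PD at Week 27 lasts about 27 weeks if duration runs to PD (counts) and about 18 weeks if it runs to the last SD scan (does not count). SD at Week 27 counts either way.

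**3. Time origin.** Scans are timed from Cycle 1 Day 1. If randomization came k days earlier, a scan on day d after first dose is day d + k after randomization. It then qualifies under section 8.7.1.1.3 when d ≥ 49 − k, which is k + 1 of the 15 days, but on only 1 of 15 under Appendix 1. Table 5 implies k = 0, so this gap should normally be small.

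**4. Size for DCR.** Inputs: PFS-4m of 55% (Arm A) and 25% (Arm B) from section 8.7.2, and 36 subjects per arm. Assumptions of this check: exponential PFS, scans on their nominal weeks, none missing, and progression-free at the scan taken as controlled. Four months = 4 × 30.4375 / 7 = 17.39 weeks, so S(t) = p^(t/17.39) with p = 0.55 or 0.25.

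| | Arm A | Arm B | Difference |
|---|---|---|---|
| S(6): Week 6 SD counts | 0.814 | 0.620 | 0.194 |
| S(12): SD needed at Week 12 | 0.662 | 0.384 | 0.278 |
| Change class, S(6) − S(12) | 0.152 | 0.236 | |
| × 36 | 5.5 | 8.5 | |

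**5. Size for durable SD.** On the same curves S(18) = 0.539 and 0.238, and S(27) = 0.395 and 0.116. The ambiguous group is 0.539 − 0.395 = 0.144 in Arm A and 0.238 − 0.116 = 0.122 in Arm B, about 5 and 4 of 36. Excluding it moves the difference from about 30.0 points to 0.395 − 0.116 = 27.9 points.

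**6. Sensitivity of the DCR difference (Week 6 counts, then Week 12 required).**
- Weibull PFS through the same 4-month rates: shape 0.5, 26.1 to 29.2 points; shape 2, 8.3 to 23.5 points.
- Arm A 90% falling to 60%, Arm B 40% falling to 28%: 50 to 32 points.
- Arm A 80% falling to 65%, Arm B 60% falling to 45%: 20 points under both.
- Equal arms at 25%: 0.620 in each arm, then 0.384 in each arm, so 0 under both.

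**The case against.** The best defence is that the cut-offs are a design choice. Seven weeks is the upper edge of the first window, so the rule may deliberately withhold credit for control shown by one early scan, and accepting SD from day 35 is a looser definition. How an SD duration ends is also commonly left to the SAP, which is not at hand. DCR and CBR are exploratory, carry no alpha, and feed no study decision.

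Much of this stands. I do not count the missing end-of-duration rule as an error in itself. But the protocol nowhere says that Week 12 confirmation is intended, and a rule with that aim would not let a day-49 scan through. The cut-offs and their starting points are fixed in the protocol text, so the mismatch with the scan windows is not an SAP detail.

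A reader might go further and infer that everyone stable at an on-time first scan is dropped and that the arm difference is inflated. The documents do not support either:
- Subjects stable again at Week 12 count. Those who fail stay in the denominator as non-controlled. If duration runs to PD, nobody is lost.
- The rule is the same in both arms and gives no difference when the arms are equal. The widening from 19 to 28 points rests on an assumed PFS curve; other curves shrink it or leave it unchanged. For durable SD, the stricter reading narrows the gap slightly.

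**Conclusion.** The point holds as a mismatch between the SD rules and the scan schedule. The 7-week minimum lies above the nominal first scan and equals the last day of its window, so under section 8.7.1.1.3 the same subject is controlled or not according to scan day. The 23-week cut-off has no scan to meet it. Appendix 1 and the endpoint section start the 7 weeks from different dates.

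If PFS is exponential through 55% and 25% at 4 months, about 5.5 of 36 and 8.5 of 36 subjects change DCR class, and the difference reads 19 or 28 points. That shows how far the reading matters; it is not an estimate of bias. PFS-4m, PFS-1y, PFS, OS and ORR do not use the SD minimum and are unaffected.

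**What to change.** In section 8.7.1.1.3, the matching synopsis text and Appendix 1:
- Measure SD from randomization throughout.
- Set the SD minimum for DCR at the lower edge of the first scan window, at least 5 weeks. Because scans are timed from Cycle 1 Day 1, which is not before randomization, every in-window first scan then qualifies. If Week 12 control is what is wanted, say so and use the lower edge of that window, 11 weeks.
- Tie durable SD for CBR to a scheduled scan less its window: SD documented at the Week 27 scan, at least 26 weeks, judged at the last scan showing SD.

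The cost is two numbers, one time origin and one clause. DCR becomes a somewhat looser measure, subjects stable at Week 18 who progress at Week 27 are settled as not durable, and comparability with studies using 7- and 23-week cut-offs is reduced.
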